  - Category 4: Pre ADA positive treatment unaffected ADA positive

All categories will be presented on the same plot (visualized using different colors). Plots will be presented using a semi-logarithmic scale for the ADA titers (ADA negative samples will therefore be excluded from the plot).

# NAb analysis

Positive ADA samples will be evaluated in a Nab assay and subjects will be classified as Nab positive or negative.

- NAb negative: no NAb positive samples at baseline or post-baseline
- NAb positive: one or more positive samples at baseline or post-baseline
- Missing: relevant NAb samples are missing, e.g. if subject had samples selected for NAb testing based on their ADA levels, but there was insufficient sample left for NAb testing.

Summary table of the incidence of NAb, defined as (cumulative) proportion of subjects having NAb positive samples at any point up to and including that time point will be summarized Missing samples will not be included in the denominator.

## Correlation of ADA and/or NAb with changed PK, PD and/or efficacy

- Individual plots of romosozumab plasma concentration ADA titer and the percent change from baseline in BMD of the lumbar spine. Each time, all three endpoints will be plotted on the Y-axes by visit (x-axis) for the full treatment period with indication of dosing time points (indication if dosing was missed), including SFU. Plots should be labeled and grouped into the pre-defined ADA subject categories as defined above. The individual plots are to be done only for categories 2 and 5.
- A summary of percent change from baseline in BMD of the lumbar spine versus time will be presented graphically including the following ADA categories (2 lines per plot).
  - Total treatment-emergent ADA positive (Category 2 and Category 5)
  - All other categories

The figure will be repeated per treatment group including placebo.

• Finally, all individual study participant-level ADA results will be listed including the results from the screening assay, confirmatory assay, and titers if applicable both and the NAb results, the ADA status, ADA subject classification and the NAb status.

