### Immunogenicity Analysis

### ADA analysis: subject classification, incidence, time of onset and time profiles

Anti-romosozumab antibodies (ADA) will be measured using a three-tiered assay approach: screening assay, confirmatory assay and titration assay.

Romosozumab

Samples will first be evaluated in the screening assay using a false positivity rate of 5% (reported as 'negative screen' or 'positive screen'), followed by analysis of screened positive samples in the confirmatory assay (which is a drug depletion assay) to confirm the true positivity of the samples (reported as 'negative immunodepletion' or 'positive immunodepletion'). Samples that are confirmed as positive will be evaluated in a titration assay to quantify the ADA level and will be reported as titer (reciprocal dilution factor including minimum required dilution).

Confirmed positive ADA samples will be subjected to an in vitro neutralizing antibody (NAb) assay.

Placebo samples will not be analysed for ADA. The summaries and figures will be done for the following analyses:

- Month 1-6 of romosozumab/romosozumab treatment group at 6-month analysis
- Month 1-12 of romosozumab/romosozumab treatment group at final analysis
- Month 1-6 of romosozumab/romosozumab group pooled with month 6-12 of placebo/romosozumab treatment group at final analysis

The ADA status should be determined for each visit where samples were taken for ADA analysis.

- Sample values that are either 'negative screen' or 'positive screen' and 'negative immunodepletion' will be defined as **ADA negative**
- Sample values that are 'positive screen' and 'positive immunodepletion' will be defined as **ADA positive**

In addition, the anti-drug antibody status will be further classified based on subject levels as outlined below. This classification should be done for entire study duration (i.e. the treatment period including SFU sampling time point).

- 1. **Pre ADA negative treatment induced ADA negative**: Includes study participants who are negative at Baseline and antibody negative at all sampling points post treatment. This group also includes study participants who have a missing pre-treatment sample (either missing or insufficient volume) at Baseline with all ADA post-treatment samples negative.

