- 2. **Pre ADA negative treatment induced ADA positive**: Includes study participants who are negative at Baseline and antibody positive at any sampling point post treatment. This group also includes study participants who have a missing pre-treatment sample (either missing or insufficient volume) at Baseline with one or more ADA positive post-treatment samples.

Confidential Page 63 of 89

- 3. **Pre ADA positive treatment reduced ADA**: Includes study participants who are positive at Baseline, and antibody negative at all sampling points post treatment
- 4. **Pre ADA positive treatment unaffected ADA**: Includes study participants who are positive at Baseline and are positive at any sampling point post treatment with titer values of the same magnitude as Baseline (ie, less than a predefined fold difference increase from the Baseline value, i.e. the minimum significant ratio (MSR) determined during assay validation).
- 5. Pre ADA positive treatment boosted ADA positive: Includes study participants who are positive at Baseline and are positive at any sampling point post treatment with increased titer values compared to Baseline (greater than a predefined fold difference increase from Baseline value, i.e. the minimum significant ratio (MSR) determined during assay validation).
- 6. **Inconclusive**: Includes study participants who have a positive or negative pre-treatment sample and some post-treatment samples are missing, while other post-treatment samples are ADA negative.

The fold difference increase (i.e. the minimum significant ratio (MSR) determined during assay validation) from baseline needed to consider a titer value reported post-treatment to be above the assay variation will be noted in the relevant tables, listings and figures.

Based on the overall ADA subject classification above, the following will be determined and presented:

- o Total prevalence of pre-Ab: n/N% number of subjects that are preADA positive.
- Total incidence of treatment-emergent ADA positive : n/N % number of subjects in category 2 and category 5

In the case that a sample is collected one or more days following the scheduled visit date in which the drug was administered, the ADA results for that sample will be associated with the scheduled visit and summarized accordingly. Such samples will also be considered when ADA results are summarized over a given study period.

The following summaries, figures and listings will be produced and will be presented using the SS.

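### The ADA-by-BMD figure in SAP 13.8 sets treatment-emergent positives against a mixed reference line, ignores when antibodies appeared, and asks for a 6-month placebo panel that cannot be defined (minor)

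*SAP*

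**What the plan says.** SAP 13.8, under the heading on correlation of ADA and/or NAb with PK, PD and efficacy, plans a plot of percent change in lumbar spine BMD against time that "will be presented graphically including the following ADA categories (2 lines per plot"). The first line is "Total treatment-emergent ADA positive (Category 2 and Category 5"). The second is "All other categories". It adds: "The figure will be repeated per treatment group including placebo".

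The category definitions come earlier in SAP 13.8. The second line collects four of them:

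- Category 1: negative at baseline (or baseline missing) and at every later sample.
- Category 3: "positive at Baseline, and antibody negative at all sampling points post treatment".
- Category 4: women who are "positive at Baseline and are positive at any sampling point post treatment with titer values of the same magnitude as Baseline".
- Category 6: inconclusive, with some post-treatment samples missing and the others negative.

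Women are classified once, over the entire study including the follow-up sample. The same section states: "Placebo samples will not be analysed for ADA". Protocol 11.7.5 likewise limits antibody testing to samples from women who receive romosozumab. After crossover, placebo/romosozumab women do have antibody results (Months 7, 9, 12 and the End-of-Study Visit).

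The other specified ADA-by-BMD output is a set of individual plots for Categories 2 and 5 only.

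**The concern.** A reader will take the second line as the antibody-negative reference. It is not: Category 4 women carry antibody while on treatment, and Category 6 women have gaps in which a positive could have been missed. If antibodies reduce the BMD response, some affected women sit in the comparator.

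The positive line has the opposite fault. Antibody samples run to Month 15 and DXA stops at Month 12. Under whole-study classification, a woman first positive at Month 9 counts as positive at Months 3 and 6, when she was still negative. The SAP handles this elsewhere: the table of immune-related TEAEs separates events before and after a woman becomes treatment-emergent positive, and has a NAb counterpart. The BMD figure has neither split, although its heading names NAb.

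The risk is that two close lines are read as showing that antibodies do not affect BMD, when the display was poorly placed to show it. The placebo panel is a separate problem: it asks for a grouping that has no data behind it at 6 months.

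**Working it through.** **What the plan gives.** SAP 13.8 states no numerical figure for this display, so there is none to reproduce. The scale is borrowed from SAP 2.6: lumbar spine difference 6.9 points, romosozumab SD 5.26, 200 romosozumab women. That section's sample size does reproduce: 146/73 gives power 0.91 at the femoral neck (difference 2.0, SDs 4.39 and 4.10), against the stated minimum of 90%. The only antibody rate in the documents is 2% neutralizing in the Phase 2 study (Protocol 2.2). Every other share below is an assumption.

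**1. Mixed reference line.** Let antibodies cost L points, and let a share c of the reference line suffer the same loss. The plotted gap is L × (1 − c). For L = 6.9 (complete loss of the assumed effect):

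| c | gap |
|---|---|
| 0 | 6.9 |
| 2% | 6.8 |
| 5% | 6.6 |
| 10% | 6.2 |
| 20% | 5.5 |

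For a half loss (3.45) with 20 positive and 180 other women, the power that a two-group comparison would have falls from 0.795 at c = 0 to 0.753, 0.707 and 0.605 at c = 5%, 10% and 20%. No test is planned; power is used here only as a gauge.

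**2. Timing.** If a share s of the positive line is not yet positive at a scan and not yet affected, the gap there is L × (1 − s). Post-baseline samples fall at Months 1, 3, 6, 7, 9, 12 and 15. Two assumed onset patterns:

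- Even over the seven samples: s = 4/7 = 57% at Month 6 and 1/7 = 14% at Month 12. A 6.9-point loss shows as 3.0 and 5.9.
- Front-loaded (25/25/20/10/10/5/5%): s = 30% and 5%. It shows as 4.8 and 6.6.

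The Month 6 shares apply only to the Month 6 point of the final-analysis figure. For the 6-month analysis, SAP 13.8 lists Months 1 to 6 of the romosozumab group, so on that scope nobody can be first positive after the Month 6 scan.

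**3. No NAb split.** If only 2% of women (4 of 200) are affected and each loses 6.9 points, the gap is 6.9 × 2%/p, where p is the share treatment-emergent positive: 2.76 at p = 5%, 1.38 at 10% and 0.69 at 20% (power 0.37, 0.20 and 0.11).

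**4. Precision.** The 95% half-width of the gap is 1.96 × 5.26 × √(1/n₁ + 1/n₂): 5.2 points with 4 positive women of 200, 3.3 with 10, 2.4 with 20 and 1.8 with 40. The SAP asks for neither n nor CI on the figure.

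**5. Placebo panel.** At the 6-month analysis the panel needs an ADA category for women whose samples are not assayed, so it is empty or undefined. At the final analysis placebo/romosozumab women can be classified, but only from samples after Month 6. Splitting their Month 3 and Month 6 BMD by that status divides placebo-period data by a later event on active drug.

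**The case against.** The strongest reply is that this is one descriptive figure, and much of the missing detail is planned nearby. Individual plots show concentration, titer and BMD by visit for every Category 2 and 5 woman; first-onset tables and Kaplan-Meier curves are planned; titer plots include Category 4; listings give each woman's ADA results, category and NAb status. That stands and keeps the severity low. It does not supply a clean group comparison, and no planned BMD display isolates Category 4.

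Several stronger readings are tempting, and the documents do not support them:

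- A reader might infer that the placebo panel also pulls the lines together. It is a separate panel and cannot move either romosozumab line.
- A reader might infer that inconclusive women left early, had fewer doses and so drag the reference line down. Category 6 is defined by missing samples, not by dosing. SAP 13.8 invokes no imputation for this figure, and SAP 4.2 leaves missing data unimputed unless otherwise specified. Any size put on such a bias would rest wholly on assumed inputs.
- A reader might call this the only check of ADA against efficacy. It is the only group-level one specified, but the text of SAP 10.4.5 breaks off in the public copy, and the Amendment 1 change log mentions optional exploratory analyses without a method.
- A reader might take the first line as all women ever positive. It is treatment-emergent positives only; of the other categories, only Category 4 is antibody-positive on treatment by definition.

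**Conclusion.** The point holds as a cheap improvement of minor severity. The reference line is not antibody-negative, and in the final-analysis figure women can be plotted as positive before they were. Each feature dilutes a real effect by the share of women misplaced, so the direction is clear and the size is not: it depends on a treatment-emergent rate, Category 4 and 6 shares and onset times that the documents do not give. If few women are in Category 4, comparator mixing matters little; timing, the absent NAb split and small numbers could matter more.

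The dilution formulas assume that Category 4 women lose as much as treatment-emergent positives and that women not yet positive lose nothing. The documents do not support saying that the figure will hide a loss of response; it could understate one.

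The 6-month placebo panel conflicts with the SAP's own assay rule and with Protocol 11.7.5, whatever the ADA rate. The primary and hierarchical tests are unaffected.

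**What to change.** In SAP 13.8:

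- Use Category 1 as the reference line. Show Categories 3, 4 and 6 separately, or list them if few.
- At each BMD visit, count a woman as positive only if her first treatment-emergent positive sample is on or before that scan. State where women not yet positive are placed.
- Flag NAb-positive women, and print n and a 95% CI per line and visit.
- Drop the placebo panel from the 6-month analysis. At the final analysis, show placebo/romosozumab women only after crossover, with BMD change from Month 6.

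No new data are needed; first-positive dates and NAb status are already planned derivations. The costs are reprogramming one exploratory figure, a slightly smaller reference group, and lines whose membership changes from visit to visit, which a footnote should state.

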# Evaluation relationship of ADA and NAb with immune related TEAE

- A summary table of all immune related TEAEs by ADA Status. For this summary, subjects will be categorized by the overall ADA subject classification and will be presented for immune related TEAEs occurring prior to becoming treatment emergent ADA positive, TEAEs occurring after becoming TE ADA positive, and TEAEs for subjects who remained TE ADA negative.
- Comparable summary table of all immune related TEAEs by NAb Status

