#### Adverse events c 10.2

Treatment emergent AEs (TEAE) are defined as all AEs started or worsened in severity on or after the date of receiving first dose of IMP and before EOS date except lipid-type AEs starting on the date of first dose of IMP and not worsening (and not deemed IMP related by the investigator). Lipid-type AEs will be defined by the Dyslipidaemia SMQ (see Appendix 13.7). The different handling of lipid-type AEs starting on the date of first dose of IMP is to ensure that pre-existing lipid abnormalities are not reported as TEAEs (lipids are only measured at Day 1 before first IMP and not at Screening).

All subsequently described displays in Section 10.2 will be compiled for the DBPC Period and for the overall study period (treatment start through Month 15). For the displays on the DBPC Period, TEAEs with a start date before or on the End of DBPC period date will be included. For the overall period, TEAEs with a start date before or on the EOS date will be included.

Duration of AEs will not be calculated if there is missing stop date information. If the intensity of an AE is unknown, it is considered as severe. If the relationship to study drug is missing, it is considered as related. Note that if the seriousness of an adverse event is unknown, every attempt should be made to resolve this prior to a snapshot for an interim analysis or database lock; in the exceptional case that the seriousness of an adverse event is still missing then no imputation should be applied for this characteristic.

If a TEAE occurs on the date of switch from the DBPC period to the OL period, the event is attributed to the DBPC treatment. The only exception that TEAEs of injection site reactions (see Appendix 13.5), potentially related to hypersensitivity (Standardized MedDRA® Query [SMQ], narrow scope) will be in OL period.

The number and incidence of TEAEs will be summarized by treatment group, the MedDRA® SOC and PT with the SOC sorted alphabetically and within SOC the PT sorted by descending order of frequencies. The incidence of TEAEs will also be summarized by treatment group (including romosozumab total), intensity and relationship to IMP.

Adverse events will be presented as "number of participants (percentage of participants) [number of events]". In this style of output, "[number of events]" will include all cases of an AE including repeat occurrences in individual participants, while "number of participants" will count each participant only once.

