### 10.2.1 Time at risk of exposure

Time at risk for each subject represents the time a study participant is at risk for having an AE with romosozumab exposure period.

In this study, time at risk (years) during the overall study period is defined as:

(End of last romosozumab – Date of the first dose of romosozumab +1) / 365.25Study participant time at risk represents the time a participant is at risk for having an AE. The definitions for time at risk (in days) are outlined in Section Error! Reference source not found.. These definitions will be used for exposure-adjusted AE summaries.

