# 10.2.2 Exposure adjusted incidence rate (EAIR) and exposure adjusted event rate (EAER)

Selected AE summaries will include the EAIR with associated 95% confidence interval and EAER where the EAIR and EAER are expressed per 100 study participant-years of exposure.

The EAIR is defined as the number of participants (n) with a specific AE adjusted for the exposure and will be scaled to 100 study participant-years:  $EAIR = 100 \times \frac{n}{\sum_{i=1}^{N} (T_{EXP(i)})}$ 

where n is the total number of participants with AE of interest, N= number of participants at risk of an AE, and  $T_{Exp(i)}$  is the total exposure time for each participant:

- For participantss with the specific AE of interest:time at risk in years to the first occurrence for the AE of interest at the level of coding evaluated
- For participantss without the AE: the total time at risk in years.

Exact Poisson 95% confidence intervals for incidence rates are calculated using the relationship between the Poisson and the Chi-square distribution (Ulm, 1990; Fay and Feuer, 1997):

$$LCL = \frac{x_{2n,\alpha/2}^2}{2}$$

$$UCL = \frac{x_{2(n+1),1-\alpha/2}^2}{2}$$

Confidential Page 39 of 89

UCB Statistical Analysis Plan 03 Mar 2023 OP0002

where n is the number of participants with a specific AE for the incidence rate of interest and is the basis for the number of the degrees of freedom for the chi-square quantile for the upper tail probability  $\chi 2$ .

The EAER will be the number of AEs including repeat occurrences in individual participants divided by the total time at risk scaled to 100 study participant-years and calculated using:

$$EAER = 100 \times \frac{N_{AE}}{\sum_{i=1}^{N} (T_{Risk(i)})}$$

where is the total number of AEs, n is the total number of participants and  $T_{Risk(i)}$  is the time at risk in years for each participant for each exposure period.

No confidence interval will be computed for EAER.

The following summaries will be provided by actual treatment group for the DBPC and the Overall Periods based on the SS. In addition, all summaries of TEAEs based on "100 participant-years" will include EAIR (with 95% confidence interval) and EAER.

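### The SAP 13.8 table of immune-related TEAEs by antibody status specifies no person-time, so its three groups can differ through unequal observation time alone

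*SAP*

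**What the plan says.** SAP Appendix 13.8, under the heading "Evaluation relationship of ADA and NAb with immune related TEAE", plans one summary table by anti-drug antibody (ADA) status. Events are divided into "immune related TEAEs occurring prior to becoming treatment emergent ADA positive, TEAEs occurring after becoming TE ADA positive", and a third group, "TEAEs for subjects who remained TE ADA negative". A comparable table is planned by NAb status. Neither entry names a denominator or a rate.

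The general rules that would fill this gap are:

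- **Display (SAP 10.2).** AEs are shown as "number of participants (percentage of participants) [number of events", closing bracket omitted here.
- **Rates (SAP 10.2.2).** "Selected AE summaries will include the EAIR with associated 95% confidence interval and EAER"; the "EAIR and EAER are expressed per 100 study participant-years of exposure". SAP 10.2.3 labels three tables as per 100 patient-years: the overview, all TEAEs by system organ class and preferred term, and serious TEAEs, each for the overall period. The antibody table is not on that list.
- **Time at risk (SAP 10.2.1).** "Time at risk for each subject represents the time a study participant is at risk for having an AE". It is a single interval over romosozumab exposure, with no break at seroconversion.
- **Windows (SAP 13.8, ADA analysis).** Three are listed. The first is "Month 1-6 of romosozumab/romosozumab treatment group at 6-month analysis". The second is Months 1 to 12 of the same group at the final analysis. The third pools Months 1 to 6 of that group with Months 6 to 12 of the placebo/romosozumab group.

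**The concern.** Women who seroconvert contribute to two groups of the table, each covering only part of their follow-up. Women who never seroconvert put all of their follow-up into the third. If the table is programmed to the default display, each percentage depends partly on how long that state lasted. The table's stated purpose is to evaluate a relationship between antibodies and immune-related events. A reader could take a difference produced by observation time for evidence of a relationship, or miss a real one that it masks. Antibody incidence is a listed safety variable in both treatment periods (Protocol 4.1.3.2 and 4.2.3.2), so the table is likely to be read closely.

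**Working it through.** The plan states no figure for this table, so there is nothing to reproduce. The check asks what the table would show if antibodies had no relationship to the events.

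**Inputs from the documents.** ADA sampling after baseline is at Months 1, 3, 6, 7, 9, 12 and end of study (Protocol 4.1.3.2 and 4.2.3.2). The listed windows are 6 and 12 months (SAP 13.8).

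**Inputs not in the documents, so assumed.** These are the rate of immune-related TEAEs, the shape of the hazard and the month of first positivity. Total follow-up is taken as equal across women.

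**Step 1: a result that needs no rate or hazard shape.** Let H(t) be the common cumulative hazard, T the window and s the month of first positivity. Then before = H(s), after = H(T) − H(s), and never-positive = H(T). Before plus after equals never-positive, so the smaller of the two is at most H(T)/2. One seroconverter group therefore expects no more than half the never-positive events per woman.

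**Step 2: after:before time ratio, (T − s)/s.**

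- 12-month window: Month 1 gives 11:1, Month 3 gives 3:1, Month 6 gives 1:1, Month 7 gives 5:7 and Month 9 gives 1:3.
- 6-month window: Month 1 gives 5:1 and Month 3 gives 1:1.

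**Step 3: expected percentages under a constant hazard λ.** Percentage = 1 − exp(−λt), with T = 1 year.

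| λ per 100 person-years (assumed) | First positive | Before | After | Never positive |
|---|---|---|---|---|
| 10 | Month 1 | 0.8% | 8.8% | 9.5% |
| 10 | Month 3 | 2.5% | 7.2% | 9.5% |
| 10 | Month 6 | 4.9% | 4.9% | 9.5% |
| 10 | Month 9 | 7.2% | 2.5% | 9.5% |
| 5 | Month 3 | 1.2% | 3.7% | 4.9% |
| 20 | Month 3 | 4.9% | 13.9% | 18.1% |

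For λ = 10 and Month 3: 1 − exp(−0.10 × 0.25) = 2.5%, 1 − exp(−0.10 × 0.75) = 7.2% and 1 − exp(−0.10 × 1) = 9.5%.

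**Step 4: sensitivity to hazard shape.** Take a 12-month never-positive incidence of 20%, so H = −ln(0.8) = 0.223, and put 60% of it in month 1. For Month 1 onset, before = 1 − exp(−0.6 × 0.223) = 12.5% and after = 1 − exp(−0.4 × 0.223) = 8.5%. The direction reverses compared with a constant hazard.

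**Step 5: simulation with no relationship.** There were 20,000 tables per scenario, with 200 or 300 women, 5% to 20% ADA positive, never-positive incidence 5% to 20%, and windows of 6, 12 or 15 months. Before and after percentages differed at least 2-fold in 41% to 84% of tables. The lower one was at most half the never-positive percentage in 72% to 87%. Part of this is chance from small ADA-positive groups. With onset spread evenly over Months 1, 3, 6, 7 and 9, 15% ADA positive, 20% incidence and a 12-month window, the mean percentages were 9.1% before, 11.8% after and 20.0% never positive.

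**Step 6: effect of using person-time.** Under a constant hazard, a state of length t has expected participants with an event 1 − exp(−λt) and expected time to first event or end of state [1 − exp(−λt)]/λ. The ratio is λ in all three states: 10 per 100 participant-years in the main example, or 22.3 if the 12-month incidence is 20%.

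**The case against.** The strongest reply is that the table is descriptive and the stakes are low. SAP 10.2.3 plans no statistical testing in the safety analyses, no efficacy endpoint is involved, and individual antibody results are listed. The only antibody frequency in the documents is 2% neutralizing in an earlier Phase 2 study (Protocol 2.2), so the NAb table may hold a handful of women. Person-time is also missing by silence and default: nothing forbids adding this table to the selected exposure-adjusted summaries. All of this stands. It limits the weight of the point but does not remove the artefact.

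A reader might infer more than the documents support:

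- **That the table is bound to show many more events after positivity than before.** It is not. Steps 3 and 4 show equal groups for Month 6 onset and a reversal for late onset or front-loaded events.
- **That the ratios are 14:1, 4:1 and 1.5:1, from following women to Month 15.** SAP 13.8 classifies women using the follow-up sample, but none of its three listed windows runs to Month 15.
- **That six months on placebo fall into the before group for placebo/romosozumab women.** TEAEs do start at first IMP (SAP 10.2), but the SAP 13.8 window list takes these women only from Month 6. The TEAE table does not say whether that list governs it, so this is an ambiguity.
- **That this is the only look at safety by antibody status.** The available text of SAP 10.4.5 breaks off mid-sentence, so this cannot be established.

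Person-time is also not a complete cure. It does not correct for a front-loaded hazard or for imprecision when few women are positive.

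**Conclusion.** The point holds as a defect of specification. Followed as written, the table compares groups with unequal time at risk and no adjustment for it. Two conclusions differ in how much they assume:

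- The halving result in step 1 needs only equal total follow-up and a common hazard.
- The size and direction of the before/after gap rest on onset timing and hazard shape, which the documents do not give. Over assumed 12-month incidences of 5% to 40% with a constant hazard, the after/before ratio of percentages is 9.0 to 10.8 for Month 1 onset, 2.7 to 3.0 for Month 3 and 1.0 for Month 6. It is 0.34 to 0.38 for Month 9.

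When events are rare the absolute gaps are small. No confirmatory result is affected. The change is worth making because it is cheap and the table otherwise cannot serve its stated purpose.

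**What to change.** Amend SAP 13.8 for this table as follows:

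1. Split each woman's time from first romosozumab dose at her first treatment-emergent ADA-positive sample.
2. Report participants and events per 100 participant-years, using the EAIR and EAER of SAP 10.2.2, for three states: before positivity, after positivity and never positive. Show the person-time for each.
3. State that the analysis windows listed in SAP 13.8 apply to the TEAEs, so that placebo-period time is not counted.
4. For the NAb table, define onset as the first post-baseline NAb-positive sample, report baseline positives separately, and apply the same split. The present NAb classification is ever-positive and includes baseline, so it gives no onset time.
5. Keep the table descriptive, with a note that the rates do not adjust for a hazard that changes over time.

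The cost is a few lines of SAP text and some extra derivation. The rates are already defined, and the time of first ADA positivity is already needed for the Kaplan-Meier display in SAP 13.8. The split of time at risk and the NAb onset date are new. Rates will be imprecise if few women are positive.
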